For the first 5 patients in this pilot we mainly test the technical feasibility of the eHealth infrastructure and evaluate the stakeholder experience. This is essential because this study differs from previous Box projects in several ways. First, our patient population is expected to be generally older compared to previous studies and will likely have substantial physical or cognitive disabilities as a result of the stroke which may lead to a reduced adaptation to the self-monitoring and use of eHealth devices. Second, this is the first Box-related project in which the Box is used to facilitate the transfer between hospital and home care. Therefore the transfer to and communication with GPs, i.e. feasibility of setting up a collaboration with multiple practices, will have to be evaluated.

In the remaining 50 patients, we evaluate the clinical implementation where we will collect data as a basis for the power calculation in the future trial. In this protocol we will describe the setup of this pilot study.

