3. STUDY DESIGN

In this pilot study we will evaluate the technical feasibility and clinical implementation of the Stroke Box in a small prospective cohort. After providing the Stroke Box to the patients, detailed information will be provided on the use of the Stroke Box and the patient will be helped with their first use.

The patient will use the Stroke Box to take at-home measurements for six months. Here we will be gathering data on blood pressure management, cardiac rhythm, patient engagement and have a user-based evaluation of the eHealth infrastructure. Patients will perform regular home measurements which the GP can use at the regular visits, and a nurse specialist in the LUMC will assess ECG measurements. We will keep close contact with both patient and GP to help in case of any questions. The patients will have access to the LUMC Box Support helpdesk who are an established customer service desk to help with any Box-related issues. We will ask the patients and GPs to contact us in case of any questions they might have. At the end of the pilot the user evaluation will be done through a questionnaire.

During the regular GP visits after the stroke related hospital admission, the GP and the nurse specialist will have insight in the collected data. We will evaluate the GP's experience of the data insight and technical usability using a questionnaire.

The study is estimated to take 12 months where we will have 6 months of inclusions and 6 months of follow-up.

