8.1.2 Secondary study parameters/endpoints

The secondary objectives of this study are:

- Gathering data on self-measured heart rhythm from the Withings Move ECG as an indicator of atrial fibrillation, weight and activity of patients using the Stroke Box, and performing a quality assessment of the collected data as assessed by regularity of assessments and frequency of occurrence of measurement error.
- The potential change in self-management of the patients due to the Stroke Box as measured through changes in lifestyle. This will be measured using changes in results from questionnaires on physical activity and healthy lifestyle intentions taken at the start and at the end of the study and the development of weight of the patient.

For the evaluation of physical activity we will adapt the Short Questionnaire to Assess Health enhancing physical activity questionnaire (SQUASH)²⁰, for the evaluation of healthy lifestyle intentions we will use the Healthy Lifestyle Intentions (HLI) questionnaire.

The evaluation of the self-management of the patient will be assessed by the Reach Efficacy Adoption Implementation Maintenance (RE-AIM) model with a mixed model evaluation based on the normalization process theory.²¹⁻²³

- Assessment of the patient adherence to the self-measurements and pharmacotherapeutic prophylactic therapy, using the Partners In Healthcare (PIH) questionnaire which measures how the patient manages his/her own disease. At the end of the study a comparison will be made between the group of patients who used the IkOefenZelf platform and those who did not.
- The technical implementation and patient adherence to the self-measurements by analysing how often they performed the measurements, if they experienced any problems as measured through the questions they asked during the study, and how they experienced the overall implementation as measured through the mHealth App Usability Questionnaire (MAUQ)²⁴ at the end of the study.
- User based evaluation of the technical – and workflow implementation for the GPs using the Stroke Box as evaluated with the Acceptability of Intervention Measure (AIM), Intervention Appropriateness Measure (IAM), and Feasibility of Intervention Measure (FIM)²⁵ questionnaires for healthcare professionals.

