Finally, the first ten patients with a modified Rankin Scale (mRS) ≥ 2 will receive access to the IkOefenZelf platform and will be asked to perform the practice modules on a regular basis.

Patients who smoke will also be asked to install the StopAdvisor app. This app will help them to quit smoking. The app is freely available from the IOS App Store and the Google Play Store.

Questionnaires

At the start and end of the study the patient will receive several questionnaires to evaluate their experiences with self-management, physical activity, healthy lifestyle intentions, their user experience, and their experience with eHealth. To evaluate the change in physical activity and lifestyle of the patient, they will be asked to fill out the SQUASH and HLI questionnaires at the start and end of the study. These questionnaires investigate respectively the amount of physical activity (e.g. sports) a patient has and what their intentions to a healthy lifestyle are (which includes questions on e.g. diet, smoking and alcohol use). In order to evaluate the experience of the patient with the self-management, they will be asked to fill out the PIH questionnaire at the start and the end of the pilot which measures how the patient manages his/her own disease. Finally, to evaluate the patient experience with the overall implementation of the Stroke Box, we will ask them to fill out the MAUQ questionnaire at the end of the study which includes questions on the technical ease-of-use, the general appearance and usefulness of the Stroke Box.

Moreover, we will evaluate the GP experience with the Stroke Box via the AIM, IAM and FIM²⁵ questionnaires for healthcare professionals which are four-item measures of implementation outcomes that are often considered “leading indicators” of implementation success.²⁶ An overview of the questionnaires used is given in the Table below.

Implementation will be assessed by the Reach Efficacy Adoption Implementation Maintenance (RE-AIM) model with a mixed model evaluation based on the normalization process theory.²¹⁻²³ The implementation will be evaluated from the perspective of the neurologists, GPs, practice assistant GP and patients.

Subject	Questionnaire	Estimated time
Physical activity	Short Questionnaire to Assess Health enhancing physical activity questionnaire (SQUASH) ²⁰	5 min
Healthy lifestyle intentions	Healthy lifestyle intentions questionnaire	4 min

Self-management	Partners In Health (PIH) questionnaire ¹⁸	4 min

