Patient experience	mHealth App Usability Questionnaire (MAUQ) ²⁴	4 min
GP experience	Acceptability of Intervention Measure (AIM), Intervention Appropriateness Measure (IAM), and Feasibility of Intervention Measure (FIM) ²⁵	3 min

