8.6 Follow-up of subjects withdrawn from treatment

Subjects who withdraw from treatment will be followed according to regular medical care.

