10.2 Secondary study parameter(s)

We will evaluate the change in lifestyle and user experience using qualitative questionnaires. Here we will make a quantitative comparison between questionnaires taken at the start and at the end of the study where we take into account the baseline characteristics of the patient, the type of stroke at hospital admission and whether the patient followed the IkOefenZelf modules as potential confounders.

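### The usability questionnaire (MAUQ) is scheduled only at study end: early leavers have no exit score, and the promised change in user experience has no start value

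*Combined protocol and SAP*

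**What the plan says.** **Timing of the MAUQ.** On the patient's view of the overall implementation, section 8.3 (Questionnaires) says: "we will ask them to fill out the MAUQ questionnaire at the end of the study". Section 8.1.2 gives the same timing, and section 3 agrees: "At the end of the pilot the user evaluation will be done through a questionnaire". The questionnaire table in 8.3 lists the MAUQ as the sole patient-experience instrument, at an estimated 4 minutes. SQUASH, HLI and PIH are taken at both start and end, but they cover physical activity, lifestyle intentions and self-management.

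**Change in user experience.** Section 2 has a secondary objective on potential change that names user experience alongside self-management and engagement. Section 10.2 states: "We will evaluate the change in lifestyle and user experience using qualitative questionnaires", and continues: "Here we will make a quantitative comparison between questionnaires taken at the start and at the end of the study". The opening sentence under Questionnaires in 8.3 also lists user experience among the topics asked about at both time points.

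**Patients who leave.** Section 8.4 lets patients leave at any time for any reason, section 8.5 rules out replacement, and section 8.6 says: "Subjects who withdraw from treatment will be followed according to regular medical care". None of the three mentions an exit questionnaire or a recorded reason for stopping. Section 10.1 will describe the dropout rate. Section 8.1.2 also counts how often patients measured and uses the questions they asked as a sign of problems.

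**Expected difficulty.** Section 1 anticipates an older population with physical or cognitive disabilities, "which may lead to a reduced adaptation to the self-monitoring and use of eHealth devices".

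**The concern.** User experience is part of the pilot's overall aim (Summary, Objective), and section 10.1 places user-based evaluation of the infrastructure among the primary-parameter analyses. The patients who could say most about whether the Box is too hard to use after a stroke are those who give it up, and they are the ones likely to lack a MAUQ score. A good score from patients still present at six months could carry an unrecognised usability problem into the planned randomised trial.

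The second issue is separate. If the plan promises a start-to-end result for user experience without collecting a start value, the analyst must either drop the result or put another questionnaire in its place once the data are in.

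**Working it through.** **1. Can a change in user experience be computed?** Set the instruments against their timing:

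| Instrument | Topic | Start | End |
|---|---|---|---|
| SQUASH | physical activity | yes | yes |
| HLI | lifestyle intentions | yes | yes |
| PIH | self-management | yes | yes |
| MAUQ | patient experience | no | yes |

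Named user-experience instruments with a start value: 0 of 1. The change cannot be formed from the planned data. Section 8.3 also disagrees with itself: its opening questionnaire sentence puts user experience at start and end, while its later sentence gives the MAUQ at the end only. This step needs no assumption.

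**2. How far could a completers-only mean be off?** The documents give no dropout rate, score gap, SD or target precision for the MAUQ, so there is no figure of the plan's own to reproduce. The only input taken from the documents is n = 55 (section 4.4). The assumed inputs are dropout share d = 5%, 10%, 20% and 30%, and a gap g = 0.5, 1.0 and 1.5 SD by which leavers would have scored worse than completers.

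All-patient mean = (1 − d) × completer mean + d × leaver mean, so the overstatement of the completer mean is d × g. Number of completers = 55 × (1 − d). Standard error in SD units = 1/√(number of completers).

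| d | No MAUQ | Completers | Overstatement at g = 0.5 / 1.0 / 1.5 (SD) | Standard error (SD) |
|---|---|---|---|---|
| 5% | 2.8 | 52.2 | 0.025 / 0.05 / 0.075 | 0.138 |
| 10% | 5.5 | 49.5 | 0.05 / 0.10 / 0.15 | 0.142 |
| 20% | 11.0 | 44.0 | 0.10 / 0.20 / 0.30 | 0.151 |
| 30% | 16.5 | 38.5 | 0.15 / 0.30 / 0.45 | 0.161 |

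At the mild corner (5%, 0.5 SD) the overstatement is 0.025/0.138 = 0.18 standard errors, which is negligible. At a 1 SD gap it is 0.20/0.151 = 1.3 standard errors with 20% dropout and 0.30/0.161 = 1.9 with 30%. With a 1.5 SD gap it already reaches 0.15/0.142 = 1.1 standard errors at 10% dropout. The standard error serves only as a yardstick here; the plan specifies descriptive statistics and no interval for the MAUQ.

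**The case against.** The strongest reply is that leavers are not invisible. Measurement frequency and the questions patients ask are captured until the day they stop, the dropout rate is reported, and section 8.3 adds a RE-AIM evaluation that includes the patient perspective. This stands, and it rules out the inference that leavers are not measured at all. What they lack is a usability score and a stated reason for leaving, and none of these sources is planned to supply either.

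A reader might also infer from section 8.6 that study contact ends when a patient stops using the Box. The section does not say so, and nothing says that a patient who merely stops measuring counts as withdrawn; such a patient could still be sent the end questionnaires. An exit MAUQ is not excluded. But nothing provides for one either.

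Nor does section 1 predict dropout. It says adaptation may be reduced, and the link from there to leaving is an inference. Section 4.2 lowers the risk by requiring a smartphone the patient can use and by excluding severe aphasia. Section 8.4 covers leaving for any reason, including urgent medical ones, so not every leaver is a usability failure.

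Finally, section 10.2 can be read as change in lifestyle, plus user experience as a separate item. That reading fits section 3, but it does not remove the objective in section 2 or the opening questionnaire sentence of 8.3.

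**Conclusion.** The point holds on two counts.

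First, with no exit MAUQ or recorded reason for stopping, the usability score will mainly describe completers and is probably too favourable. The direction rests on leavers finding the Box harder to use than completers do, which section 1 makes plausible but does not establish. The size cannot be derived from the documents: about 0.03–0.45 SD under the assumed ranges, from trivial to nearly three standard errors (0.45/0.161 = 2.8).

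Second, a start-to-end change in user experience cannot be computed, and sections 2, 8.3 and 10.2 need to be reconciled. This rests on the text alone.

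The documents do not support reading this as a defect in the blood pressure results or in any power figure: the affected endpoint is secondary and descriptive. It should be corrected because it bears on the overall aim and the remedy is cheap.

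**What to change.** - **Sections 8.3 and 8.6:** offer the MAUQ and one question on the reason for stopping to every patient who stops, through the app or by phone from the existing helpdesk. The phone route matters for those who found the app difficult.
- **Section 8.6:** distinguish stopping use of the Box from withdrawing consent, and still ask patients who only stop using it for the end questionnaires.
- **Section 2, the opening questionnaire sentence of 8.3, and section 10.2:** drop *change* for user experience. Report the MAUQ at end or exit descriptively, for all respondents and separately for completers and leavers, with time of use and the number of leavers who did not respond. Adding a MAUQ before first use would not help, because patients would have nothing to rate.

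The cost is a short amendment and about 4 minutes, plus one question, for each patient who stops. Some leavers will decline, so the gap narrows rather than closes. Exit scores will also reflect differing lengths of use, which is why time of use should be shown beside them.

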8.4 Withdrawal of individual subjects

Subjects can leave the study at any time for any reason if they wish to do so without any consequences. The investigator can decide to withdraw a subject from the study for urgent medical reasons.

8.5 Replacement of individual subjects after withdrawal

If a subject decides to withdraw from the study, they will not be replaced.

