4.4 Sample size calculation

In the LUMC there are 450 stroke patients per year, 50-60% of which are immediately discharged home. Of these patients we expect 85% willing to sign the informed consent form and have the GP willing to cooperate in the pilot. We will be including patients for a maximum of 6 months, in this time there will be about 105 potential patients for our study according to our calculations. We will be including 55 patients. We will use this patient population to estimate incidence of blood pressure out of the therapeutic window (>140mmHg) for the power analysis of a future clinical trial.

In 37.5% of patients, we expect to see a change in blood pressure in 6 months,¹⁴ this would amount to 20 patients in our population of 55 patients. This would be sufficient to power a future trial focusing on blood pressure measurements using the Stroke Box infrastructure. Earlier studies focussing on long term recording of heart rhythm in patients with cryptogenic stroke found occult atrial fibrillation in 9% to 16% of patients.^{3,15} As 87% of stroke patients have ischemic strokes¹⁶ and about a third of those have cryptogenic strokes, we expect to find cryptogenic strokes in about 29% of the LUMC stroke population.¹⁷ Therefore, we expect around two to three patients in which we would detect atrial fibrillation after hospital discharge. This would be the minimum to power a future trial focussing on atrial fibrillation detection using the ECG smartwatch. In conclusion, 55 patients amounts to the minimum size we would need to obtain sufficient results.

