10. STATISTICAL ANALYSIS

10.1 Primary study parameter(s)

We will use descriptive statistics to assess blood pressure management, patient engagement and user-based evaluation of the eHealth infrastructure. We will analyze their self-measurement frequency of blood pressure, heart rhythm, weight, and activity using the mean measurements per week. The dropout rate will be described and the change in blood pressure in mmHg. This will be used as a basis for sample size calculation for future trials.

Moreover, we will use descriptive statistics to assess the clinical characteristics of our sample population.

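### Section 4.4 enrols exactly its stated minimum of 55 and bases its expected counts on all 55, with no allowance for dropout

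*Combined protocol and SAP*

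**What the plan says.** Section 4.4 of the combined protocol and SAP fixes enrolment: "We will be including 55 patients". It expects the following from that number.

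- **Blood pressure:** "In 37.5% of patients, we expect to see a change in blood pressure in 6 months", and "this would amount to 20 patients in our population of 55 patients". It adds that this is enough to power a later trial.
- **AF:** long-term recording in cryptogenic stroke "found occult atrial fibrillation in 9% to 16% of patients", and "we expect to find cryptogenic strokes in about 29% of the LUMC stroke population". From these it expects two to three detections after discharge, and calls that count the least that would support powering an AF trial.
- **Overall:** "In conclusion, 55 patients amounts to the minimum size we would need to obtain sufficient results".

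On patients who leave, section 8.4 allows a subject to stop at any time. Section 8.5 says "If a subject decides to withdraw from the study, they will not be replaced". Section 8.6 returns those who withdraw to regular care and plans no further study measurement. Section 10.1 says "The dropout rate will be described and the change in blood pressure in mmHg". Neither section 4.4 nor any other section gives an expected dropout rate or says that 55 already contains a margin.

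**The concern.** The number to be enrolled and the number said to be the minimum are the same, so the plan has no slack. The main endpoint (8.1.1) is a before-after comparison of self-measured blood pressure, and the 37.5% in 4.4 refers to a change over six months. A patient who stops measuring early has no six-month value. Some loss is likely: section 1 expects an older group, with disabilities that may make the devices harder to use, and section 10.1 treats dropout as something to report.

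At stake is how section 4.4 will read beside the final report. The pilot exists to supply planning figures for a randomised trial. If its report shows ordinary attrition, the expected counts and the claims that they are adequate will not match what was delivered. No hypothesis test is affected, because section 10.1 is descriptive.

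**Working it through.** **Inputs.** From section 4.4: 55 enrolled; 37.5% with a blood pressure change in six months; 29% cryptogenic; 9% to 16% occult AF among those. From section 8.5: no replacement. Dropout d is not given, so 10%, 20% and 30% are assumed.

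**Step 1: reproduce the plan's figures with no dropout.**

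- Blood pressure: 55 x 0.375 = 20.6. The plan says 20, so this reproduces.
- AF: 55 x 0.29 x 0.09 = 1.44 and 55 x 0.29 x 0.16 = 2.55, that is 1.4 to 2.6. The plan says two to three, which needs the lower end rounded up from 1.4.

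Both calculations use all 55, with no attrition factor.

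**Step 2: one withdrawal.**

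- Blood pressure: 54 x 0.375 = 20.25, still 20.
- AF: 54 x 0.29 x 0.09 to 0.16 = 1.41 to 2.51.
- The effect is nominal.

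**Step 3: how much loss the 20 can absorb.** 20 / 0.375 = 53.3, so 54 of the 55 must have six-month data for the expectation to stay at 20 or more. With 53 it is 53 x 0.375 = 19.9, and with 50 it is 18.75. If patients leave independently, the chance that none of 55 leaves is 0.95^55 = about 6% at 5% dropout and 0.90^55 = about 0.3% at 10%.

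**Step 4: a range of dropout.** Patients with six-month data: n = 55 x (1 - d). Expected blood pressure changes: n x 0.375. Expected AF detections if leavers contribute none: n x 0.29 x 0.09 to n x 0.29 x 0.16.

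| Assumed dropout | With six-month data | Expected BP changes | Expected AF detections (worst case) |
|---|---|---|---|
| 0% | 55 | 20.6 | 1.4 to 2.6 |
| 10% | 49.5 | 18.6 | 1.3 to 2.3 |
| 20% | 44 | 16.5 | 1.1 to 2.0 |
| 30% | 38.5 | 14.4 | 1.0 to 1.8 |

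**Step 5: effect on precision.** The 95% half-width around 37.5% is 1.96 x sqrt(0.375 x 0.625 / n). It is 12.8 percentage points at n = 55, 12.9 at 54 and 14.3 at 44.

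**Step 6: the base.** Section 1 says the data for the power calculation come from the 50 patients after the first five. The Summary suggests that the first five also serve the other objectives. On a base of 50 with 20% dropout, 50 x 0.8 = 40 patients and 40 x 0.375 = 15 changes, against 44 and 16.5 on a base of 55.

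**The case against.** A reader might infer that sections 4.4 and 8.5 contradict each other, so that the first withdrawal takes the study below its own minimum. The documents do not support that. The Summary and section 4.4 both give 55 as the number included, and the sentence that calls 55 the minimum can be read the same way. On that reading a withdrawal leaves 55 included and nothing is breached. Planning to report dropout, expecting some difficulty with the devices and not replacing leavers are also compatible, and in a feasibility pilot dropout is a legitimate outcome. Step 2 shows that one loss leaves the expected 20 intact.

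Three further objections limit the numbers.

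- The 37.5% comes from a cited study, and the documents do not say whether its denominator was everyone enrolled or only those followed to the end. If it was everyone enrolled, multiplying by (1 - d) counts attrition twice and the reduced blood pressure counts do not apply.
- AF can be detected before a patient leaves, since section 8.3 asks those with suspected AF to record daily. The reduced AF counts are therefore a worst case.
- The AF shortfall at the low end exists with full retention, so section 8.5 does not cause it.

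The loss of precision is also small (step 5).

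All of this stands. What remains is that 4.4 does not say what its 55 counts, makes no allowance for loss, and draws conclusions about adequacy from counts that assume almost none.

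**Conclusion.** The point holds as a minor one. Section 4.4 sets enrolment equal to its stated minimum and makes no allowance for attrition that other sections foresee and do not make good. The expected 20 blood pressure changes need at least 54 of 55 patients with six-month data. At an assumed 10% to 30% dropout the expectation is 18.6 down to 14.4. That rests on two assumptions the documents do not settle: the dropout range itself, and that the 37.5% applies to patients with six-month data.

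The AF figure needs correcting whatever the dropout. The plan's own inputs give 1.4 to 2.6 with everyone retained, so the lower end already falls short of the two to three that 4.4 treats as its floor. If leavers contribute no detections, the range at 30% dropout is 1.0 to 1.8, wholly below two.

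The rule in 8.5 is not itself wrong for a descriptive pilot. The weakness is in the claims made beside it.

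**What to change.** Keep 55 enrolled and keep the no-replacement rule. In section 4.4:

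1. State that 55 is the number enrolled.
2. Give the expected number with six-month blood pressure data, and the expected counts, under a stated dropout range. For example, at 20%: 44 patients and 16 to 17 changes. Say that this takes the 37.5% to apply to patients with six-month data, or say what its denominator is.
3. Correct the AF expectation to about 1.4 to 2.6 before dropout.
4. State whether the base is all 55 or the 50 patients after the first five, and use that base throughout (at 20% dropout, 50 gives 40 patients and 15 changes).
5. Remove or qualify all three adequacy statements: that 55 is the minimum size, that the AF count is the minimum for powering a trial, and that the blood pressure count is enough to power one. Changing only the first would leave the same claim standing in the other two.

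The cost is a wording change in 4.4. Enrolment, conduct and analysis stay as they are, and the stated figures become slightly less favourable.
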